2.4 Pooling Strategy for Strata

No pooling will be done.

2.5 Safety Analyses

Safety endpoints will be summarized with descriptive statistics. All safety summaries and analyses will be performed using the safety population.

Prior and Concomitant medications will be coded by the World Health Organization (WHO) Drug Dictionary version September 2012.

Adverse Events and Medical History will be coded using MedDRA version 20.1.

2.6 Statistical/Analytical Issues

2.6.1 Handling of Dropouts or Missing Data

Summary statistics will be reported based upon observed data. Additionally, if the start date of an AE or concomitant medication is incomplete or missing, it will be assumed to have occurred on or after the infusion of ALD403, except if an incomplete date (e.g., month and year) clearly indicates that the event started prior to treatment.

2.6.2 Multicenter Studies

Data from all sites will be pooled for presentation.

2.6.3 Interim Analyses

This study will include a formal interim analysis after all subjects have completed the primary treatment phase (i.e. approximately a year after the last subject enters the study).

3 STATISTICAL SUMMARIES

3.1 General Conventions

Unless otherwise stated, summary statistics including the number of subjects (n), mean, standard deviation, median, minimum and maximum will be presented for continuous variables.

Generally, the minimum and maximum values will be presented to the same decimal precision as the raw values, the mean and median values to one more, and the standard deviation, to two more decimal places than the raw values. This decimal place convention may be followed for all data elements. For categorical variables, per category, the absolute counts (n) and percentages (%) of subjects with data, and if appropriate, the number of subjects with missing data, will be presented. Percentages will be presented to one decimal place.

For PK data, the following applies:

Concentration values for free ALD403 will be presented as received from the Bioanalytical Laboratory.

Values for all PK parameters and for mean concentrations will be presented in three or four significant digits, as appropriate, i.e., 3 significant digits for minimum and maximum, 4 significant digits for mean, SD and median; % CV is given to 1 decimal point.

For AEs, medical history and concomitant medications reported on a per-subject basis, the denominator for the percentage calculation will be the number of subjects at risk. A subject will be considered at risk if the subject is in the analysis set and in the subgroup of interest.

Unless otherwise specified all safety as well as demographic and baseline characteristic analyses will be based upon the safety population and all PK analyses will be based upon the PK population.

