1.1 Objectives

1.1.1 Safety Objective

The primary objective is:

- To evaluate the long term safety of repeat doses of ALD403 administered intravenous (IV) in patients with chronic migraine.

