1.2 Clinical Trial Design

This is an open label trial which will include two treatment phases. The primary treatment phase will include four intravenous infusions of 300mg ALD403 in patients with chronic migraine. Infusions will be 12 weeks apart. The secondary treatment phase will include four additional 300mg ALD403 infusions 12 weeks apart. Subjects who provide informed consent will be evaluated for eligibility based upon the inclusion and exclusion criteria.

Eligible subjects will receive 4 IV infusions of 300mg ALD403 in the primary treatment phase on Days 0 (11-14 days after the screening visit), 84 (Week 12), 168 (Week 24) and 252 (Week 36). Subjects who receive all 4 infusions in the primary treatment phase may enter the secondary treatment phase, where subjects will receive up to 4 additional infusions for a total of 8 infusions. The infusions in the secondary treatment phase will occur on Days 336 (Week 48), 420 (Week 60), 504 (Week 72) and 588 (Week 84). Subjects will be followed for 20 weeks until Week 104 for a total study duration of approximately 106 weeks, including the screening period. Subjects who don't receive all 4 infusions of ALD403 in the primary treatment phase or don't consent for participation in the secondary treatment phase will be followed at Week 48 and Week 56, at which point they will have their End of Trial visit.

Approximately 120 subjects will be enrolled and treated. Study specific assessments will be conducted according to the Schedule of Events presented in [Table 1: Schedule of Events and Assessment](#).

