1.3 Sample Size

The planned sample size for this study is 120 treated subjects. It is assumed that over 75% of these subjects will complete the primary treatment phase resulting in at least 90 subjects with one year of safety data collection.

TABLE 1: SCHEDULE OF EVENTS AND ASSESSMENT

Assessments	Screening Day -14 to -11	Day 0	Wk 2 Day 14 ± 3 days	Wk 4 Day 28 ± 3 days	Wk 8 Day 56 ± 3 days	Wk 12 & 24 & 36 Day 84 / 168 / 252 ± 3 days	Wk 48 Day 336 -7/+14 days	Wk 60 & 72 & 84 Day 420 / 504 / 588 ± 7 days	Wk 56 ⁹ or 104 EOT / Early Withdrawal Day 392 or 728 ± 7 days
Informed Consent, Demographics, Medical History, Height	X								
In/Ex Criteria	X	X							
Weight	X	X				X			X
Physical Exam ¹	X	X				X	X ¹¹	X	X
Vital Signs ³	X	X				X	X	X	X
C-SSRS ^{4,1}	X	X	X	X	X	X	X	X	X
PGIC ²				X	X	X	X	X	X
SF-36, HIT-6 ¹	X	X		X		X	X	X	X
EQ-5D-5L ¹²	X	X		X		X	X		X ¹⁰
MBS	X	X		X	X	X	X		X ¹⁰
MIDAS ¹		X				X	X	X	X
AE/ Con Med Review	X	X	X	X	X	X	X	X	X
ALD403 infusion ⁵		X				X	X ¹¹	X	
12-lead ECG ⁷	X	X				X	X	X	X
Hematology, Chemistry ¹	X	X				X	X	X	X
HIV/Hepatitis B and C	X								
Plasma PK ^{6,8}		X	X	X	X	X	X		X
Serum Anti-ALD403 ⁶		X	X	X	X	X	X		X
Urine Drugs of Abuse ¹	X								
Urine Pregnancy Test	X	X		X	X	X	X	X	X

¹ Conduct assessment pre-dose on Day 0 and Week 12, 24, 36, 48, 60, 72, and 84.

² Conduct assessment pre-dose on Week 12, 24, 36, 48, 60, 72, and 84.

³ Conduct assessments pre-dose and up to 2 hours (+ 30 min) post-dose on Day 0 and Week 12, 24, 36, 48, 60, 72, and 84.

⁴ Conduct **C-SSRS Baseline/Screening Version** at screening and **C-SSRS Since Last Visit Version** at remaining visits where C-SSRS required.

⁵ Monitor subjects for at least 2 hours after the end of each dosing to assess for the occurrence of adverse events.

⁶ Collect samples pre-dose on Day 0 and Week 12, 24, 36, 48, and 72. Subjects who test positive for anti-ALD403 antibodies at the last study visit will be asked to provide up to 2 additional blood samples for immunogenicity testing at 3 month intervals for up to 6 months.

⁷ Conduct assessment pre-dose, and within 2 hours (+ 30 min) post dose on Day 0 and Week 12, 24, 36, 48, 60, 72, and 84.

⁸ On Day 0, collect additional sample immediately post-dose (within 15 minutes of end of infusion).

⁹ Subjects who don't received all 4 infusions of ALD403 in the primary treatment phase or don't consent to participate in the secondary treatment phase will have the End of Trial/Early Withdrawal visit at Week 56.

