3.3 Clinical Trial Subjects

3.3.1 Subject Disposition

The number of subjects signed informed consent, treated, discontinued Investigational Product early, and terminated from the clinical trial early will be summarized. The reason for early discontinuation of Investigational Product or termination from the clinical trial will be summarized. Additionally, the summary of subjects present at each visit will be summarized. Subjects enrolled but not included in the safety analysis population and the reasons for exclusion will be summarized. The number of subjects screened and summary of screen failure reasons will also be summarized.

A listing of entry criteria that were not met will be produced.

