3.3.6 Clinical Trial Treatment

Total volume infused, number of infusions and reason for dose interruption will be listed as well as summarized in a table.

3.4 *Efficacy Analyses*

The secondary endpoints of patient reported outcomes (PROs) will be summarized with descriptive statistics by time point. These summary measures will be based upon the observed results and where appropriate the change from baseline results. The denominator for percentages will be the total number of PROs collected at each visit since not all subjects will complete PROs at all visits.

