3.6 Analysis of Safety Endpoints

3.6.1 Adverse Events

Adverse events are collected from the time of Informed Consent through the final subject visit. The incidence of all AEs and study drug-related AEs will be tabulated. These AEs will be classified by system organ class and preferred term using the MedDRA. For incidence reporting, if a subject reported more than 1 AE that was coded to the same preferred term/system organ class, the subject will be counted only once for that specific preferred term/system organ class. Events recorded between the time the informed consent is signed and the first Investigational Product administration will be listed.

A treatment-emergent AE (TEAE) is an AE with a start date and time on or after the date and time of the initial treatment.

For the purpose of inclusion in TEAE tables, incomplete AE onset and end dates will be imputed as follows:

Missing onset dates (where UK and UKN indicate unknown or missing day and month respectively):

- **UK-MMM-YYYY:** If the month and year are different from the month and year of the first dose of trial drug, assume 01-MMM-YYYY. If the month and year are the same as the first dose of trial drug month and year, and the end date (after any imputation) is on or after the first dose of trial drug, then assume the date of the first dose of trial drug. If the month and year are the same as the first dose of trial drug month, and year and the end date (after any imputation) is prior to the first dose of trial drug, then assume the end date for the onset date.
- **DD-UKN-YYYY/UK-UKN-YYYY:** If the year is different from the year of first dose of trial drug, assume 01-JAN-YYYY of the collected year. If the year is the same as the first dose of trial drug year, and the end date (after any imputation) is on or after the first dose of trial drug, then assume the date of the first dose of trial drug. If the year is the same as the first dose of trial drug, and the end date (after any imputation) is prior to the first dose of trial drug, then assume the end date for the onset date.

Missing end dates (where UK and UKN indicate unknown or missing day and month respectively):

- **UK-MMM-YYYY:** Assume the last day of the month;
- **DD-UKN-YYYY/UK-UKN-YYYY:** Assume 31-DEC-YYYY.

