An overview of AEs, which includes subject incidence of TEAEs, study drug-related TEAEs, serious TEAEs, TEAEs leading to treatment withdrawal, TEAEs leading to treatment interruption, TEAEs leading to discontinuation and deaths will be presented.

The subject incidence of TEAEs and study drug-related TEAEs will be summarized by system organ class and preferred term.

Treatment-emergent AEs will also be summarized in a table by severity. For TEAEs presented by severity, the worst severity for each event during the clinical trial will be presented for each subject.

All AEs will be presented as a listing by subject. This listing will include the duration of the AE.

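### The planned AE tables give one crude percentage over unequal follow-up and do not separate primary-phase from secondary-phase events

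*SAP*

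**What the plan says.** **Objective.** SAP 1.1.1 states the primary aim: "To evaluate the long term safety of repeat doses of ALD403" in chronic migraine. AEs are the first-listed safety endpoint (SAP 2.2), and Protocol 5.4 acknowledges that long-term data are limited.

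**Denominator.** For AE percentages, SAP 3.1 says: "A subject will be considered at risk if the subject is in the analysis set and in the subgroup of interest". The safety population is everyone with at least one dose (SAP 2.1). No phase or exposure subgroup is defined.

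**Numerator and layout.** Under SAP 3.6.1, for repeated AEs with the same coding, "the subject will be counted only once for that specific preferred term/system organ class". The main tables are specified as follows: "The subject incidence of TEAEs and study drug-related TEAEs will be summarized by system organ class and preferred term". The severity table takes the worst grade over the trial. AEs of special interest (AESIs, SAP 3.6.2.1) are broken down by severity, relationship, infusion interruption, discontinuation and seriousness. Serious AEs follow the TEAE layout (SAP 3.6.2.2). The infusion-associated AESIs have a one-week window after dosing but are pooled over all infusions.

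**Follow-up.** Under SAP 1.2, subjects who miss a primary-phase infusion or decline the secondary phase "will be followed at Week 48 and Week 56, at which point they will have their End of Trial visit". The others may receive up to eight infusions and are followed to Week 104. SAP 1.3 assumes over 75% complete the primary phase, "resulting in at least 90 subjects with one year of safety data collection".

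**Exposure summaries.** SAP 3.3.1: "Additionally, the summary of subjects present at each visit will be summarized". SAP 3.3.6: "Total volume infused, number of infusions and reason for dose interruption will be listed as well as summarized in a table". Neither is linked to AEs.

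**The concern.** Infusions five to eight are the part of this trial that speaks most directly to long-term repeat dosing. Their AEs are merged into the same ever/never count as those of infusions one to four, over a denominator that still includes subjects whose planned follow-up stopped at Week 56. This has two consequences:

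- An AE that first appears in the second year is divided by people who were no longer being observed, so the printed percentage is lower than the incidence among those still at risk.
- The final table looks the same whether events fall in the first or the second phase.

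The first consequence depends on how many subjects continue. The second does not. Up to Week 56 planned follow-up is the same for everyone, so the denominator problem concerns the second year, apart from ordinary dropout.

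**Working it through.** **1. The plan's own figures.** 120 × 0.75 = 90, as stated in SAP 1.3. Last infusion plus 20 weeks: 84 + 20 = 104 for eight infusions, and 36 + 20 = 56 for four. These agree with Days 728 and 392 in the schedule (728/7 = 104; 392/7 = 56).

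**2. AEs first arising after Week 56.** Let n be the number of the 120 followed to Week 104 and p the risk after Week 56 among them. The table shows n × p / 120, which is n/120 of p. The understatement is 1 − n/120.

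**3. AEs at constant hazard.** Take a 10% risk over 104 weeks as an example. The weekly hazard is −ln(0.9)/104, so the 56-week risk is 1 − 0.9^(56/104) = 5.52%. The crude percentage is [n × 10% + (120 − n) × 5.52%] / 120.

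The documents do not give n, so a range is shown. It is assumed that everyone who does not continue reaches Week 56 and everyone who continues reaches Week 104.

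| n to Week 104 | Late AEs appear at | Understatement | A 10% risk appears as |
|---|---|---|---|
| 120 | 100% | 0% | 10.0% |
| 114 | 95% | 5% | 9.8% |
| 90 | 75% | 25% | 8.9% |
| 60 | 50% | 50% | 7.8% |

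The 90 in SAP 1.3 is a floor for primary-phase completers. It is not a forecast of secondary-phase uptake, which could be lower or higher.

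**4. Early against late onset.** Cut at the Week 48 infusion, where the secondary phase starts. Assume 90 subjects continue, 52-week years, one event per affected subject and no censoring at the event. Weeks 48 to 56 of the 30 non-continuing subjects count as primary-phase follow-up.

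- Primary-phase patient-years: (120 × 48 + 30 × 8)/52 = 6,000/52 = 115.4.
- Secondary-phase patient-years: 90 × 56/52 = 96.9.
- Total: 115.4 + 96.9 = 212.3.

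Suppose nine subjects have a given event:

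| Summary | All nine in primary phase | All nine in secondary phase |
|---|---|---|
| Crude table | 9/120 = 7.5% | 9/120 = 7.5% |
| Overall rate per 100 patient-years | 9/212.3 = 4.2 | 9/212.3 = 4.2 |
| Primary-phase incidence | 9/120 = 7.5% | 0/120 |
| Primary-phase rate per 100 patient-years | 9/115.4 = 7.8 | 0 |
| Secondary-phase incidence | 0/90 | 9/90 = 10.0% |
| Secondary-phase rate per 100 patient-years | 0 | 9/96.9 = 9.3 |

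Neither the crude percentage nor a single overall patient-year rate separates the two patterns. Only the within-phase figures do.

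**The case against.** The case for leaving the plan as it is has real substance.

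- **The crude percentage is legitimate.** It answers what share of treated subjects reported an event. The analysis is descriptive and single-arm, so no treatment contrast is biased. This stands.
- **The denominator rule could accommodate phases.** Its wording would allow a phase to be the subgroup. But the SAP names none, and no AE table asks for one.
- **There is an interim analysis.** SAP 2.6.3 plans one after all subjects complete the primary phase, and comparing it with the final tables might partly separate early from late events. The help is only partial: its AE content and data cut are not stated, early enrollees may already be in the secondary phase, and it is cumulative.
- **Time is not ignored elsewhere.** Labs and antibodies are summarized by visit, and vital signs and ECG by measurement day (SAP 3.6.3 to 3.6.5). AEs are listed by subject and onset dates are collected (Protocol 11.1.3). So what is missing is a summary, not data. A listing, though, gives no incidence.
- **Counts will be small.** Secondary-phase cells by preferred term will be sparse. This limits precision but does not argue against showing them.

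Two stronger readings are tempting. A reader might infer that late AEs will be badly understated. The documents do not support this, because uptake is not given and at 114 of 120 the loss is only 5%. A reader might also infer that a by-phase table would show whether risk changes with repeat infusions. It would not settle that: secondary-phase subjects have received all four infusions and consented, AEs can lead to discontinuation (Protocol 8.4.1), and there is no comparator.

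**Conclusion.** The point holds for the planned AE tables. They give one crude percentage with no split by phase or dosing interval and no person-time, while planned follow-up ends at either Week 56 or Week 104. The understatement for AEs first arising after Week 56 equals the share of subjects not continuing: 0% to 50% across the assumed range of 120 down to 60 continuing. It rests on the simple follow-up pattern assumed above.

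The inability of the final AE tables to separate early from late onset needs no assumption about retention. It bears directly on the primary objective. It does not make the planned percentages wrong, and it concerns the AE tables rather than the data collected. It is a worthwhile, inexpensive improvement to make before database lock.

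**What to change.** Keep the crude tables and add the following.

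- **SAP 3.6.1 and 3.6.2:** incidence of TEAEs, serious TEAEs and AESIs by treatment phase, classified by onset date. The primary phase runs from Day 0 to before the Week 48 infusion, and the secondary phase from that infusion to Week 104. Assign Weeks 48 to 56 of non-continuing subjects in advance to primary-phase follow-up.
- **Counting:** each subject once per term per phase, with subjects under observation at the start of the phase as denominator. Also report events per patient-year within each phase, since the phases differ in length between subjects.
- **SAP 3.3.6:** a follow-up-duration summary giving the numbers reaching at least 52 and at least 104 weeks. The first figure also checks the one-year target in SAP 1.3.
- **Interpretation note:** state that secondary-phase rates describe subjects who received all four primary-phase infusions and consented, so a lower late rate is not by itself evidence of falling risk.

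The cost is SAP wording and a few tables, with small secondary-phase counts. The dates needed are already collected. Trial conduct and sample size do not change.

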3.2 Definition of Baseline

The baseline assessment will be the latest available valid measurement taken prior to the administration of Investigational Product. This will generally be Day 0.

3.3 Clinical Trial Subjects

3.3.1 Subject Disposition

The number of subjects signed informed consent, treated, discontinued Investigational Product early, and terminated from the clinical trial early will be summarized. The reason for early discontinuation of Investigational Product or termination from the clinical trial will be summarized. Additionally, the summary of subjects present at each visit will be summarized. Subjects enrolled but not included in the safety analysis population and the reasons for exclusion will be summarized. The number of subjects screened and summary of screen failure reasons will also be summarized.

A listing of entry criteria that were not met will be produced.

3.3.2 Analysis Population

The number of subjects in each analysis population will be summarized.

3.3.3 Demographics and Baseline Characteristics

Demographic, baseline characteristics, migraine history and concomitant medications (coded by the World Health Organization Drug Dictionary) will be summarized descriptively.

3.3.4 Prior and Concomitant Medications

Medications with a stop date before the treatment dosing date will be considered prior medications. Medications with a start or stop date on or after the treatment dosing date will be considered concomitant medications. All medications marked as ongoing are concomitant medications.

A medication with an incomplete stop date will be considered concomitant if:

- Month is missing and year is equal to or after the year of treatment dosing date
- Day is missing and year is equal to the year of the treatment dosing date and month is equal to or after the month of the treatment dosing date.

Concomitant medications will be summarized. All medications will be provided in a listing.

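### SAP 3.3.4's rule for stop dates with only the day missing leaves out later calendar years, so the concomitant-medication summary can omit background drugs stopped on study (minor)

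*SAP*

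**What the plan says.** SAP 3.3.4 gives three general rules. A drug that ended before dosing is prior. For the concomitant class it says: "Medications with a start or stop date on or after the treatment dosing date will be considered concomitant medications". A drug still being taken also counts as concomitant.

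It then gives two conditions under which an incomplete stop date puts a drug in the concomitant class. When the month is unknown, the condition is: "Month is missing and year is equal to or after the year of treatment dosing date". When only the day is unknown, the condition is narrower: "Day is missing and year is equal to the year of the treatment dosing date and month is equal to or after the month", where the month meant is that of dosing.

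Only concomitant drugs go into a summary, while every drug goes into a listing.

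SAP 2.6.1 deals with start dates: "if the start date of an AE or concomitant medication is incomplete or missing, it will be assumed to have occurred on or after", with the infusion as the reference point. Its one exception concerns partly recorded start dates: "except if an incomplete date (e.g., month and year) clearly indicates that the event started prior to treatment". Protocol 13.2.2 carries the same rule. Neither place compares the assumed start with a known stop date.

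**The concern.** The two partial-date bullets do not match. The month-missing bullet reaches forward to any later year, but the day-missing bullet stops at the end of the dosing year. A more complete date can therefore fail where a less complete one passes, and the SAP gives no reason for this.

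The records affected are narrow but not random. A drug started on study is caught by its start date, and an ongoing drug is caught by the ongoing rule. What remains is a drug known to have been in use before Day 0 and stopped during the study. Protocol 9.3 lets stable prophylaxis continue and, after Week 48, lets it be changed by the Investigator or the treating professional, so such stops are foreseen. In a single-arm, open-label trial, the concomitant-medication summary is where a reader looks for background treatment during ALD403 exposure.

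The second, smaller issue is that a missing start date assumed to fall on or after the infusion can contradict a known stop date before it.

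**Working it through.** No sample-size or error-rate formula applies. The check is to run dates through the rules as written. I take the treatment dosing date to be the first dose.

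**Step 1. Partial stop dates, illustrative first dose 15-MAR-2017, drug started earlier and not ongoing**

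| Recorded stop | Bullet that applies | Meets it as written? | Meets it if month and year are compared together? |
|---|---|---|---|
| UK-DEC-2016 | day missing | no | no |
| UK-FEB-2017 | day missing | no | no |
| UK-MAR-2017 | day missing | yes | yes |
| UK-SEP-2017 | day missing | yes | yes |
| UK-JAN-2018 | day missing | **no** | yes |
| UK-NOV-2018 | day missing | **no** | yes |
| UK-FEB-2019 | day missing | **no** | yes |
| year 2018 only | month missing | yes | unchanged |

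The three bold rows are plainly after dosing, yet they fail. The year-only 2018 record, which says less, passes.

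**Step 2. How much of follow-up lies in the uncovered years**

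Inputs: follow-up from Day 0 to Day 728 (Week 104) is 729 days counted inclusively. For subjects ending at Week 56 (Day 392) it is 393 days. Assumption: first doses spread evenly over a 365-day year. A first dose on day k of the year leaves 366 − k days in the dosing year, which averages 183.

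- Week 104: (729 − 183)/729 = 546/729 = 75% of follow-up days fall in a later year. The range is 364/729 = 50% (dosing on 1 January) to 728/729, nearly 100% (31 December).
- Week 56: (393 − 183)/393 = 210/393 = 53%. The range is 28/393 = 7% to 392/393, nearly 100%.

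For the period after Week 48 no enrolment assumption is needed. Day 336 to Day 728 is 393 days. Even with a first dose on 1 January, Day 336 is 3 December in a non-leap year, so 29 of those days fall in the dosing year (30 in a leap year). At least 363/393 = 92% therefore lies in a later year for any dosing date.

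These are shares of follow-up time, not of medication records.

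**Step 3. Does the corrected rule work?**

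Running every calendar month from dosing to Week 104, for all 365 dosing dates, through the corrected rule leaves none missed. Months before dosing are still not concomitant. Under the rule as written, about 74% of those subject-months fail.

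**Step 4. Missing start date with a known pre-dose stop**

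First dose 15-MAR-2017, stop 20-JAN-2017, start missing. By its stop date the drug is prior under SAP 3.3.4. If SAP 2.6.1 is applied, the start is assumed to be 15-MAR-2017 or later, and the drug also meets the concomitant definition, with a start after its own stop. The exception in SAP 2.6.1 looks only at what an incomplete start date shows, so it does not help. For adverse events, SAP 3.6.1 does check the end date: where the event ended before first dose, onset is set to the end date. With the same check here, the drug is prior only.

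**The case against.** The strongest answer on the first issue is that the general sentence in SAP 3.3.4 already settles it. Every possible day in January 2018 is after a March 2017 dose, so the stop date is on or after dosing whatever the missing day is. The bullets also say when a medication is concomitant, not that these are the only cases. This stands in part, and it is why exclusion is not certain. However, the bullets were written specifically for incomplete stop dates, and a program built from them would drop these records. If the general sentence were meant to cover obvious later-year dates, the month-missing bullet would not have needed to mention later years.

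On the second issue, a reader might infer that a drug stopped before dosing simply turns concomitant. The documents do not support that. SAP 3.3.4 still calls it prior, and SAP 2.6.1 speaks of the start date of a concomitant medication, so it is unclear that the rule reaches a drug already classed as prior. What stands is that both definitions can be met and no precedence is given.

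A reader might also take the 75% as the share of stop dates that go wrong. It is not. That would further require stop dates spread evenly over follow-up, and the number of partial dates is not given. Protocol 9.3 requires medication dates to be recorded and the Schedule of Events reviews concomitant medication at every visit, so partial on-study stop dates may be few.

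Finally, no t-test, adverse-event table, PK or immunogenicity analysis in the SAP depends on the prior or concomitant class, and every medication is listed. This objection stands in full and sets the severity.

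**Conclusion.** The point holds as a minor drafting defect. Taken literally, the day-missing bullet misses on-study stop dates in any calendar year after the dosing year, while the month-missing bullet catches the less complete version of the same date. The concomitant-medication summary can therefore omit background drugs stopped on study. The documents do not show that it will: the general sentence may be applied instead, and the number of affected records cannot be estimated from the documents. The secondary defect is a possible dual classification without a precedence rule.

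It would go too far to say that the table is wrong in both directions. That needs the least favourable reading of both rules together with partial dates in unknown number. The effect is limited to one descriptive summary.

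**What to change.** 1. In SAP 3.3.4, replace the day-missing bullet with: *Day is missing and the month and year are equal to or after the month and year of the treatment dosing date.*
2. In SAP 3.3.4, or as a medication rule in SAP 2.6.1, add: *A medication with a stop date known to be before the first dose is prior, regardless of a missing or incomplete start date.* The wording should rest on a known stop date, because the SAP defines end-date imputation for adverse events but none for medication stop dates.

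The cost is two sentences and a small change to the medication-classification program, best made before the tables are produced. No new data and no change to any test are needed.
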